Recruitment script at time of referral & Referral Confirmation/Welcome Email

The recruitment process begins with a welcome email that is sent by the program. From here, interested individuals may click on a link in the referral confirmation/welcome email and self-proceed to review the online consent form and enroll in the study. For those who do not complete this step prior to their admission intake (typically 24-48 hours from receipt of referral), a clinician will follow up to inquire about their interest during this meeting. Those indicating interest at that point will be directed to the same information via email. For those with no email address, permission will be obtained from patients by a clinician for a research team member to reach out for the purposes of discussing the study and enroll over the phone. The first month of the study will be a feasibility period to test out our recruitment strategies. The researchers will seek feedback and suggestions to troubleshoot recruitment barriers from the clinical team members and the PCAC during this time. Recruitment strategies will be adjusted as required.

Data Collection

Data will be collected through self-report surveys at designated time points, as well as chart review to collect service delivery and healthcare utilization data.

Participant Incentives. Participants will be offered honoraria as incentives for study participation. Participants will be offered \$5 gift cards at each follow-up data collection time points (Time 2, 3, and 4). Gift cards will be administered electronically (unless physical cards are requested) by the RA.

Variables & Data Sources/Measures

Variables of interest for the study include participant demographics, along with service delivery, recovery, and systems use outcomes.

Demographic Variables (Time 1). The Demographic Questionnaire and SINCERE questionnaire will be completed at Time 1 (admission). The demographic questionnaire will include variables related to sociodemographic information: age, gender, education, income, employment status, relationship status, living situation, urban/rural residence, race/ethnicity, and clinical reason for referral/diagnosis. The data will be collected from participant self-report.

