Recovery Outcomes (Time 1, 2, 3, and 4). Recovery will be measured using 2 questionnaires that were co-selected with input from the PCAC: the **WHO-5 Well-Being Index** and the Maryland Assessment of Recovery Scale- 12 item (MARS-12). The Who-5 Well-Being Index is a 5-item measure that assesses subjective psychological well-being" (Topp et al., 2014, p. 167). It has been used to monitor global recovery among psychiatric inpatients showing good sensitivity to change with an established MCID that correlates to other validated measures of psychiatric impairment (Topp et al., 2014). MARS-12 is a shortened version of the MARS-24 designed to measure recovery orientation among individuals with mental illness (Drapalski et al., 2012).

Service Delivery Outcomes (Discharge). Service delivery outcome data are: length of stay, and outcome of stay (discharge, transfer to in person CSU/hospital, emergency activation, and lost

to follow-up. These data will be provided by the clinical team lead as a report approximately monthly.

Systems Use Outcomes (Time 1, 2, 3, 4). Systems use outcomes will include: CRC use, Emergency Department use, and psychiatric hospitalizations. We will collect both self-report and health administrative data to assess for recall bias and to enable some systems use outcomes for individuals who are lost to follow-up in the study. At baseline, systems use in the 3 months prior to admission will be collected. At time 1 and 2, we will collect systems use since discharge from the MH vWard. At time 4, we will collect prior 1-month utilization, including if they utilized the MH vWard again during that time period. Self-report systems variables will be collected using a modified version of the Service Utilization based on the **Client Service Receipt Inventory (CSRI)**. Corresponding health administrative data will be extracted from the electronic medical records of participants by a research team member. Reliable health administrative data will only be available for Winnipeg-based participants as few rural health care facilities utilize the available electronic medical records (most are paper-based).

Time Points

Data will be collected at 4 different time points:

Time 1 (baseline):

- Participants are to complete baseline questionnaires within 72 hrs of admission
- If a participant does not complete questionnaires within 72 hrs of admission, the participant will be excluded from further data collection.

Time 2 (primary outcome):

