- Participants are administered questionnaires 1 week AFTER discharge, with + 1 week of leeway for completion (within 7-14 days of discharge).

Time 3 (secondary outcome):

- Participants are administered questionnaires 5 weeks AFTER discharge, with +/- 1 week of leeway for completion (within 4-6 weeks of discharge).

Time 4 (secondary outcome):

- Participants are administered questionnaires 6 months AFTER discharge, with a +/- 2 weeks of leeway for completion (within 6 months -2 weeks and 6 months +2 weeks).

	Time 1 (admission)	Discharge	Time 2 (1 week post discharge)	Time 3 (5 weeks post discharge)	Time 4 (6 mos post discharge)
Demographic data (Demographic Questionnaire; SINCERE)	X				
Recovery outcomes (WHO-5,	X		X	X	X

MARS-12; Global Recovery Questions)					
Service Delivery outcomes (Data capture sheet)		X			
Systems use outcomes (Service Utilization; data capture sheet)	X		X	X	X

- For self-report surveys at Time 1, 2 and 3, data may be collected through the Telus HHM App as they will also be utilized for assessment and care planning purposes (for those utilizing the App as part of their care), RedCap (for those not utilizing the App), or by phone or in person, for those with this preference or who lack an email/internet connection. All participants will complete questionnaires at Time 4 on REDCap.

Participants completing questionnaires electronically (Telus, REDCap) will receive up to 2 reminders by phone or email at Time 2, 3, and 4, if needed.

Participants completing questionnaires over the phone or in person with the RA will receive up to 2 phone calls to connect for the purpose of completing the questionnaire together.

All data entered into the Telus HHM App for consenting participants will be output in an electronic report by a clinical team member and shared with the research team. The research team member will then manually enter these responses into the REDCap survey.

Data Storage

Clinicians will upload PDF reports containing questionnaire responses generated from the Telus App into a shared folder on the Shared Health Network drive, accessible by the PI. The PI will generate hard copies of the reports for the RA to extract the data from. Once data are manually entered into REDCap and verified, hard copies will be destroyed using confidential shredding. All responses will be stored in REDCap along with identifying data and consent information.

Statistical Analyses

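### As written, the 72-hour baseline rule also ends collection of service-delivery and record-based outcomes that need no questionnaire, and so can select on those outcomes

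*Combined protocol and SAP*

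**What the plan says.** Under Time Points, Time 1 (baseline), questionnaires are due within 72 hours of admission, and then: "If a participant does not complete questionnaires within 72 hrs of admission, the participant will be excluded from further data collection". No exception follows.

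The Data Collection section describes two routes, self-report surveys "as well as chart review to collect service delivery and healthcare utilization data". The table under Time Points lists record items beside the questionnaires: "Service Delivery outcomes (Data capture sheet" and "Systems use outcomes (Service Utilization; data capture sheet".

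The service-delivery outcomes are "length of stay, and outcome of stay (discharge, transfer to in person CSU/hospital, emergency activation, and lost" to follow-up). Their source is the clinical team: "These data will be provided by the clinical team lead as a report approximately monthly".

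Systems use is collected by self-report and from health records. One stated reason for the records is "to enable some systems use outcomes for individuals who are lost to follow-up in the study". The section adds a limit: "Reliable health administrative data will only be available for Winnipeg-based participants".

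**The concern.** A rule meant to secure a baseline score is worded so that it removes the participant from everything that follows. A pre-post WHO-5 comparison needs a baseline, so leaving these people out of that analysis is right. The service-delivery report and the record extraction do not need one.

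The people most likely to miss a questionnaire in the first 72 hours may include those transferred to in-person care, those for whom emergency services were activated, and those who dropped out of contact. These are categories of the outcome-of-stay variable. If they are dropped because of the event, the reported frequency of the event is computed in a group selected on it.

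The results at stake are the descriptive service-delivery outcomes and, for Winnipeg participants, record-based systems use. The Introduction also intends the cohort as a historical comparator for later evaluation, so any selection could carry forward.

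**Working it through.** **Does the text reach record data?**

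- The rule's object is the participant, and what stops is data collection without qualification.
- Data Collection defines that activity as surveys plus chart review.
- The Time Points table includes data capture sheets for service delivery and systems use.
- No sentence limits the rule to surveys, keeps record data for these people, or plans a comparison of baseline completers with non-completers.
- Under Eligibility, every admission qualifies and nothing is excluded, so baseline completion is not an entry condition.

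**Can a listed outcome cause the exclusion?** The typical stay is 5 days (Exposure to Intervention), so 72 hours covers 3 of 5 days. An early transfer, emergency activation or loss of contact can fall in that window. Several features lower the risk: enrolment can precede intake, App surveys double as care assessments, and phone or in-person completion allows up to 2 calls. They do not remove it. Electronic reminders are stated for Times 2, 3 and 4, not Time 1.

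**The plan's own figure.** Sample Size expects 700 admissions and allows for up to 15% declining: 700 × 0.85 = 595, as stated. This is the only documented input below. The documents give no rate of missed baselines or early events, so every other value is an assumption.

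**Worst-case bounds.** Let m be the share of consenters dropped and p the event rate among those kept. The rate in all consenters lies between (1 − m)p, if no dropped person had an event, and (1 − m)p + m, if all did.

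| p | m | Lower | Upper |
|---|---|---|---|
| 10% | 5% | 9.5% | 14.5% |
| 10% | 10% | 9.0% | 19.0% |
| 10% | 20% | 8.0% | 28.0% |
| 5% | 10% | 4.5% | 14.5% |
| 20% | 10% | 18.0% | 28.0% |

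These are limits, not expected bias.

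**Direction.** Let E be the true event rate, q the share of people with an event who miss baseline, and r the share of the others who miss it.

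- Share missing = Eq + (1 − E)r
- Reported rate = E(1 − q) / (1 − share missing)

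Take E = 10%. All three cases have 14% missing, and 0.14 × 595 is about 83 people.

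- q = 50%, r = 10%: missing 0.05 + 0.09 = 0.14; reported 0.05 / 0.86 = 5.8%.
- q = r = 14%: reported 0.086 / 0.86 = 10.0%, no bias.
- q = 5%, r = 15%: missing 0.005 + 0.135 = 0.14; reported 0.095 / 0.86 = 11.0%.

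The same number lost can therefore understate the rate, leave it unchanged or overstate it. The number missing alone will not show which.

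**The case against.** The strongest reply is that the rule was only ever about surveys. It follows a bullet on baseline questionnaires, and the other Time Points bullets on Times 1 to 4 also concern questionnaires. The incentives paragraph uses data collection to mean the survey points. Service delivery sits in a separate Discharge column, and nothing says the team lead's report is filtered by baseline completion. This makes survey-only intent plausible, more so for service delivery than for systems use, whose data capture sheet is listed at Times 1 to 4. It does not settle the matter: the sentence excludes the person, and the protocol's own description of data collection includes chart review.

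Second, being lost to follow-up in the study may mean enrolled people who later stop responding, so the rule and the purpose of the record data need not conflict. That holds for people lost after baseline. For someone who enrolled and was lost before baseline, the literal rule still defeats that purpose. Loss to follow-up as an outcome of stay is a separate item.

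Third, people without a baseline lack self-reported covariates and cannot contribute to the comparison of self-report with records. They would mainly add to unadjusted descriptive results. This stands, but descriptive summary is what the plan specifies for service delivery.

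Fourth, early events can also prevent consent, so all consented participants remain a selected group. This also stands: the change reduces selection and does not abolish it. Finally, the protocol has yet to set the requirements for the future cohort, so carry-over into later work is a risk, not a certainty.

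**Conclusion.** The concern holds in conditional form: applied as written, the rule stops collection of outcomes that need no questionnaire, and it can do so because of those outcomes. Understatement of step-up and emergency rates is the likely direction if early events cause missed baselines. Overstatement is possible if those who miss have fewer events, and there is no bias if missing is unrelated to outcome. The size cannot be estimated from the documents.

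The WHO-5 pre-post analysis and its required sample of 452 are unaffected. The systems-use part is confined to Winnipeg participants; the service-delivery part is not. Confidence is moderate, because the authors may have intended the narrower rule.

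**What to change.** Restrict the rule to questionnaire data, for example:

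> Participants without Time 1 questionnaires by 72 hours contribute no Time 1 WHO-5 or MARS-12 score and are not in the pre-post recovery analysis. They remain in the cohort for service-delivery outcomes and, if Winnipeg-based, for record-based systems use, where consent covers use of records.

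Report these outcomes for all consented participants, repeat them in baseline completers as a sensitivity analysis, and tabulate the number missing baseline by outcome of stay. That table would show whether missing baseline is related to outcome. If survey-only was always meant, the sentence simply says so.

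The cost is protocol wording plus some record extraction. The service-delivery data already arrive in the team lead's report. Extraction applies only to Winnipeg participants who miss baseline: at most about 30, 60 or 119 people if 5%, 10% or 20% of 595 miss it (assumed shares). Some self-reported covariates will be missing for them. Consent must cover record use without a baseline survey; the consent pages are not in the public text, so the investigators need to confirm this.
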